## Flow of study

[figure not shown]
## **Data analysis**

The collected data will be entry and analyzed using SPSS version 24 (SPSS Inc., Chicago, IL, USA)

Objective 1 is to determine and compare gastric residual volume between group A and group B subjects. Independent T test is used to interpret the date.

Objective 2 is to determine and compare subject's well being before and after drink in between group A and group B. paired t test is used to determine effect of drink on subject's wellbeing before and after in each group. ANOVA is used to compare effect of the drink in both groups.

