Traditionally, adequate fasting time with a minimum of 6 hours is required before operation in order to prevent pulmonary aspiration during general anaesthesia. Lately, allow clear fluid for up to 2 hours prior operation is recommended as it improve patient's wellbeing and it is safe(Kratzing, 2011). However, not all solution is safe to be used as carbohydrate loading. Type of food (solid or fluid), the volume of fluid, particle size and composition of the fluid can affect gastric emptying rate (Dalal *et al.*, 2010; Nygren *et al.*, 1995). With the presence of carbohydrate and protein, gastric emptying rate is shorter than fluid contain fat or cellulose(Dalal *et al.*, 2010). Polymer carbohydrate such as maltodextrin has low osmolality which cause rapidly passage of fluid through stomach if compare with monomer fluid(Nygren *et al.*, 1995). According to previous study, 400cc of carbohydrate rich solution (12.0% carbohydrate, maltodextrin) was used and it took about 90minutes to pass through stomach (Nygren *et al.*, 1995). Hence, carbohydrate loading with polymer is recommended in order to provide large dose of carbohydrate which able to stimulate insulin release and not produce significant gastric residual volume prior to anaesthesia.

Kaska et al. (2010) conducted a randomized, prospective and blinded clinical trial, in which patients were randomized into three groups: overnight fasting group as control group, intravenous administer glucose preoperatively and preoperative oral consumption of 400cc a specifically composed solution (principally maltodextrin and electrolytes). Gastric residual volume was examined by aspiration of juice with the aid of a gastric tube inserted temporarily at the beginning of surgery. It showed that the residual volume was 5 ml in all groups without statistically significant differences. However, the values

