of gastric residual volume perioperatively was smallest in preoperative carbohydrate drink group. Yagci et al. (2008) had conducted similar study, in which patient was randomized into 2 groups that were overnight fasting and carbohydrate drink(800cc on the evening before and 400cc 2 hours prior to operation), it showed no statistically significant difference between two groups with respect to gastric residue contents. Itou et al. (2011) conducted a study which randomized patient into 2 group that were fasting group and ORS group showed similar result. However, study conducted by Dalal et al. (2010) randomized patient into 2 groups that were fasting (group I) and water (group II). It showed that the gastric fluid volume was found to be lesser in Group II ( $5.5 \pm 3.70$  ml) than Group I ( $17.1 \pm 8.2$  ml) which was statistically significant.

Significant gastric residual volume can predispose to pulmonary aspiration for patient undergo general anaesthesia. Pulmonary aspiration is defined of inhalation of solid or liquid into respiratory tract(Nason, 2015). It occurs 1 in 900 to 1 in 10000 of patient underwent general anaesthesia(Robinson and Davidson, 2014). General anaesthesia is considered safe in most of the cases, but pulmonary aspiration can cause significant airway related mortality and morbidity(Nason, 2015). Entry of acidic gastric content into lung leads to pneumonitis. The severity of the injury to lung parenchymal is depend on gastric volume, pH level of aspirated gastric content and content of the aspirated fluid which cause infection or mechanical airway obstruction(Nason, 2015). Traditionally, patient is considered as high risk of aspiration pneumonia if gastric volume aspirated more than 25cc and pH less than 2.5(Dalal *et al.*, 2010). There are several normal physiological reflex mechanism presences in order to prevent aspiration which include gastroesophageal junction, upper oesophageal sphincter and protective laryngeal reflex(Robinson and Davidson, 2014). However, these protective reflexes abolished after general anaesthesia due to the drug used during anaesthesia. Apart from the causes above, systemic disease such as diabetic mellitus also affect gastric emptying time.(Asai, 2004)

In addition to metabolic effect due to carbohydrate loading, patient's well being such as hunger, thirst, anxiety can be improved also(Hausel *et al.*, 2001).

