## **Methodology**

### **Research design**

This is a stratified (female, male) with balanced randomisation (1:1), single-blind (blind endoscopist, researcher enrolling and assessing participants), placebo-controlled, parallel-group study

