### **Sample size estimation**

Sample size is calculated for all the objectives. However, the one that yield the biggest number is taken as the sample size.

objective 1 is to identify the gastric residual volume between subject with plain water (group A) and carbohydrate loading (group B). Sample size was calculated using comparing two means formula. Sample size is calculate using <http://www.openepi.com/SampleSize/SSMean.htm>. The ratio between group A and group B was set as 1. According to article, standard deviation was 18.46. Means difference was set as 12.5. sample size for objective 1 is 35 per group.

Objective 2 is to determined patient's well being for group A and group B. sample size was calculate using comparing paired difference formula. Sample size calculate using <http://statulator.com/SampleSize/ss2PM.html#>. Expected standard deviation of the paired

differences is set as 2 times the expected mean of the paired differences. The sample size is 34 per group

For all sample size calculation, type I error was set at 5% (two tailed), Type 2 error was 20% (to achieve 80% power of study).

Corrected sample size is calculated after included 10% of dropout rate. Corrected sample size = calculated sample size/ (1-anticipated drop out rate).

After considering both objective, 1st objective give biggest number of sample size. Hence, 35 subject per group with a total number of 70 subjects are needed to study both objectives. after consider dropout rate, minimum sample size in this study is 39 subjects per group with a total number of 78 subjects.

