### **Sampling method and subject recruitment**

Patient scheduled for elective OGDS in HUSM from April 2019 to December 2019 with the complaint of one or more of the following symptoms: Botherome postprandial fullness, early satiation, Epigastric pain or Epigastric burning are eligible to participate in the study. Patients who fulfilled exclusion criteria (History of upper gastrointestinal surgery, intestinal obstruction, patient with vomiting or mentally disable or who cannot give an informed consent) are ineligible.

If a patient fulfils the inclusion criteria, a suitable medical officer will discuss the trial with patient while reviewing patient in surgical outpatient clinic prior to OGDS. Patient will be approached again on the day of OGDS, if patient agree to participate in study, a written consent will be obtained. If patient refuse to participate in study, appropriate treatment and care still will be provided to patient. The consent form will provide information about the purpose of the study, the procedures to be followed,

risks and benefits of participation. If patient agree to participate in the trial, subject will be enrolled in the study. Method of recruitment in this study is direct recruitment of potential study participants.

Stratified permuted block randomization was used. Randomization sequence was created using <https://www.sealedenvelope.com/simple-randomiser/v1/lists> and is stratified by gender (female and male) with 1:1 allocation. Random block sizes of 6 is used. Subjects are randomized into either preprocedure plain water (group A) or preprocedure carbohydrate loading group (group B). Patients randomized into group A consume 250ml plain water and patients in group B consume 1 packet of resource (237ml, 53.6g carbohydrate and 9g whey protein). Both groups of patients consume the drink over 10 minutes. 2 hours after that, OGDS will be carried out.

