**Expected result**

Patient's characteristic

	Group 1 (plain water) (n=)	Group 2 (resource) (n=)
Age (y)		
Gender (female/male)		
Body mass index (kg/m  )		

Data presented in means (SD) or number of subject)

Residual gastric volume in both group

	Group 1 (plain water) (n=)	Group 2 (resource) (n=)
Residual gastric volume (ml)		

Data presented in means (SD)

Visual analogue scale data for preprocedure discomfort variables

VAS variable		Before drink mm, median (IQL)	Before OGDS mm, median (IQL)
Hunger	Group 1		
	Group 2		
Thirst	Group 1		
	Group 2		
Anxiety	Group 1		
	Group 2		
Weakness	Group 1		
	Group 2		
Tiredness	Group 1		
	Group 2		

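### Randomisation is stratified by sex, but the primary t-test ignores sex: valid as it stands, with a small gain in precision available at almost no cost

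*Protocol*

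**What the plan says.** The Research design section of the Protocol describes the trial with the words "This is a stratified (female, male) with balanced randomisation (1:1". Sampling method and subject recruitment repeats this for the allocation list: "stratified by gender (female and male) with 1:1 allocation. Random block sizes of 6 is used".

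For the primary end point, residual gastric volume in ml, the Data analysis section names one method: "Independent T test is used to interpret the date". It has no term for sex. The Sample size estimation section rests on the same unadjusted comparison: "Sample size was calculated using comparing two means formula", with the inputs "According to article, standard deviation was 18.46. Means difference was set as 12.5".

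Sex is recorded on the pro forma and has its own row, "Gender (female/male", in the planned table of patient characteristics. No part of the Protocol says whether sex is related to residual volume, and none promises an analysis adjusted for sex.

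**The concern.** Stratified blocks keep the sexes balanced between the groups. Differences between men and women then contribute almost nothing to the true sampling variation of the mean difference. The ordinary t-test does not use this fact: it still counts between-sex variation in its standard error. If sex explains a share R² of the variance of residual volume, that standard error is too large by about 1/√(1−R²).

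The error goes in the safe direction, with fewer false positives than 5% and a confidence interval wider than it need be. What is at stake is some precision that the design has already paid for. The planned power has no slack at 35 evaluable patients per group. A covariate has to be named in advance, because adding it after the data are seen would look selective.

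**Working it through.** **Inputs from Sample size estimation:** SD 18.46 ml, difference 12.5 ml, two-sided α 5%, power 80%, ratio 1:1, dropout 10%.

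**Assumptions not in the document:** half the patients are women; R² for sex is 0, 0.02, 0.05 or 0.10; 18.46 ml is the total SD; the groups are balanced within sex.

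**Step 1. The plan's own figure.** n per group = 2 × (1.960 + 0.842)² × 18.46² / 12.5² = 34.2, rounded up to 35. With dropout, 35/0.9 = 38.9, rounded up to 39. Both stated figures reproduce. By the noncentral t distribution, 35 per group gives 79.7% power and 39 gives 83.9%.

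**Step 2. What each R² means in ml.** With equal numbers of each sex, the difference between sexes is 2 × 18.46 × √R² = 0, 5.2, 8.3 and 11.7 ml. For scale only, the Literature review cites one trial of fasting against water in which "the gastric fluid volume was found to be lesser in Group II"; the gap was 17.1 − 5.5 = 11.6 ml, equivalent to R² = (11.6/36.92)² = 0.099. In another cited trial "the residual volume was 5 ml in all groups without statistically significant differences". Neither compares the sexes. They suggest only that a sex difference near 12 ml would be large, so 0.10 is used as a ceiling.

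**Step 3. The two analyses at 35 per group, normal errors.**
- The standard error used by the t-test is 18.46 × √(2/35) = 4.413 ml. Its half-width is 1.9955 × 4.413 = 8.81 ml.
- The true standard error under stratification is 4.413 × √(1−R²).
- Type I error of the t-test = 2 × P(t with 68 df > 1.9955/√(1−R²)).
- Power comes from the noncentral t with noncentrality 12.5 / (4.413 × √(1−R²)). The t-test uses critical value 1.9955/√(1−R²) on 68 df, and the adjusted model uses 1.9960 on 67 df.

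| Assumed R² | t-test type I error | Power, t-test | Power, adjusted | Gain (points) | Half-width, t-test (ml) | Half-width, adjusted (ml) |
|---|---|---|---|---|---|---|
| 0 | 5.0% | 79.7% | 79.7% | 0.0 | 8.81 | 8.81 |
| 0.02 | 4.8% | 80.0% | 80.5% | 0.5 | 8.81 | 8.72 |
| 0.05 | 4.4% | 80.3% | 81.7% | 1.4 | 8.81 | 8.58 |
| 0.10 | 3.9% | 81.0% | 83.7% | 2.8 | 8.81 | 8.36 |

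**Step 4. Simulation of the actual scheme.** This used 70 evaluable patients, permuted blocks of 6 within sex (the last block possibly incomplete) and 20,000 replicates per row. The values below are for R² = 0, 0.02, 0.05 and 0.10.

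| Errors | t-test type I error | Adjusted type I error | Power gain (points) |
|---|---|---|---|
| Normal | 4.8, 4.7, 4.3, 3.8% | 4.8, 4.9, 4.8, 4.8% | 0.0, 0.6, 1.5, 2.9 |
| Exponential (skewness 2) | 4.8, 4.5, 4.3, 3.7% | 4.9, 4.7, 4.9, 4.8% | 0.0, 0.5, 1.2, 2.5 |
| Lognormal (skewness 4) | 4.5, 4.2, 3.9, 2.8% | 4.5, 4.5, 4.5, 4.2% | 0.0, 0.4, 1.2, 2.2 |

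The simulation agrees with the formulas. Under strong skew both tests are somewhat conservative even when sex has no effect, so adjustment removes only part of the shortfall.

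**The case against.** The strongest reply is that nothing here is wrong. The t-test is valid, it matches the formula used for the sample size, and it fits the planned results table of group means and SDs. No passage promises a sex-adjusted analysis, so there is no contradiction. Covariate adjustment is often settled in a statistical analysis plan, and one may exist. The benefit depends on an R² that the document does not give and that may be zero. At R² = 0.02 the gain is half a power point and 0.09 ml of half-width, against a target difference of 12.5 ml. The cited volumes used for scale compare treatment groups, not sexes, and the trial behind the 11.6 ml gap reports SDs of 8.2 and 3.70 ml, not 18.46.

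Most of this stands, and it sets the priority: the gain is likely small, the ceiling of 0.10 is a judgement, and under heavy skew adjustment does not bring the type I error fully back to 5%. It does not remove the point. The Protocol does not leave the method open. It names the primary test, and that test omits the factor by which the trial randomises. An analysis plan that added sex would depart from the Protocol's text, so the Protocol is the place for the change.

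**Conclusion.** The point holds as an optional improvement. The Protocol stratifies by sex and then fixes a primary test that ignores sex. The stated test remains unbiased, does not exceed 5% type I error and has about 80% power, and the 35 and 39 per group are unaffected. With an assumed R² of 0 to 0.10, a 50:50 sex split and a total SD of 18.46 ml, adjustment is worth 0 to 2.8 points of power and 0 to 0.45 ml of half-width (8.81 − 8.36). The lower part of that range is the more credible. If the plan is left as it is, the analysis is still valid.

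**What to change.** In the Data analysis section, replace the sentence on the t-test with:

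> Residual gastric volume is compared between groups with a linear model with group as factor and gender (the randomisation stratification factor) as covariate; the adjusted mean difference with 95% CI and two-sided p value is reported. The independent t-test is a sensitivity analysis.

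This needs no new data field and no change in sample size. If sex turns out to explain nothing, the price is one degree of freedom (68 to 67): the critical t goes from 1.9955 to 1.9960, the half-width from 8.806 to 8.808 ml and power from 79.74% to 79.73%.

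### The wellbeing plan treats before/after change within each arm as the effect of the drink, and its 80% power belongs to that paired test, not to carbohydrate versus water

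*Protocol*

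**What the plan says.** The Data analysis section defines objective 2 as determining and comparing the subject's "well being before and after drink in between group A and group B". Two analyses follow. First, a "paired t test is used to determine effect of drink on" wellbeing, before versus after, in each group. Second, "ANOVA is used to compare effect of the drink in both groups"; the form of the ANOVA is not given.

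For objective 2, the section Sample size estimation says "sample size was calculate using comparing paired difference formula". The standard deviation of the paired "differences is set as 2 times the expected mean of the paired differences", and the result is 34 per group. Two-sided 5% error and 80% power apply to all the calculations. Objective 1 (gastric residual volume, two-means formula) gives 35 per group, and the section concludes that "35 subject per group with a total number of 70 subjects are needed to study both objectives". Allowing for 10% dropout gives 39 per group, 78 in total.

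In Expected result, the table headed "Visual analogue scale data for preprocedure discomfort variables" has a median column before the drink and one before OGDS for each group, and no column for a between-arm difference.

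**The concern.** Between the two VAS assessments every subject has the drink, waits two hours without food in the endoscopy room, and comes closer to the procedure. A paired test within one arm responds to all of these together. Only the comparison of the randomised arms removes what they share and leaves the drink.

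The protocol's own Literature review shows that the mixing is plausible. In the 210-patient study all five of this trial's scales rose in the fasting arm, which had no drink. In the carbohydrate-drink arm hunger rose over time although that arm was less hungry than the fasting arm, so its within-arm trend taken alone would have suggested the opposite of the between-arm result. In the 252-patient study tiredness rose in the flavoured-water arm, the one nearest to this trial's control, but also in the fasted arm. This evidence has limits: both studies used trend analyses rather than paired t tests, the 210-patient comparator was fasting rather than water, and the directions do not always conflict. In the 252-patient study hunger and anxiety fell within the carbohydrate arm and were also lower than in the other arms.

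Two misreadings follow. A significant paired test could be reported as an effect of carbohydrate, or of water, when it shows only that scores changed over the wait. And the stated 80% power could be taken to cover carbohydrate versus water on wellbeing, for which it was never calculated.

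**Working it through.** **Inputs from Sample size estimation.** Two-sided 5%; 80% power; SD of paired differences = 2 × their mean, so the standardised within-arm change is 1/2 = 0.5; 34 per group for objective 2; 35 per group before dropout.

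**Step 1: the protocol's own figure.** For a paired test the noncentrality is d√n on n − 1 degrees of freedom. The normal approximation gives ((1.960 + 0.842)/0.5)² = 31.4; adding the small-sample term 1.960²/2 = 1.92 gives 33.3, hence 34. By the exact noncentral t:

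| n in the arm | Power, paired test, d = 0.5 |
|---|---|
| 33 | 79.5% |
| 34 | 80.8% |
| 35 | 82.0% |

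So 34 is right, for one arm's before/after test.

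**Step 2: the comparison that objective 2 names.** The difference between two mean changes has standard error SD√(2/n), against SD/√n for a single arm's change. With 35 per arm the noncentrality is δ√(35/2) on 68 degrees of freedom, where δ is the between-arm difference in SDs of change. The protocol gives no such difference, so δ is an assumption shown over a range:

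| δ (SD of change) | Power, 35 per arm |
|---|---|
| 0.5 | 54% |
| 0.6 | 70% |
| 0.68 | 80% |
| 0.8 | 91% |

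At δ = 0.5 the noncentrality is 0.5 × √17.5 = 2.09, against 0.5 × √34 = 2.92 for the paired test. Reaching 80% at δ = 0.5 would take 64 per arm.

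**Step 3: the same comparison by ANCOVA**, adjusting for before-drink score and sex (66 degrees of freedom). Let a single VAS score have SD 1 and let r be the before/after correlation (assumed). The SD of change is √(2(1 − r)) and the residual SD is √(1 − r²). For r = 0.5 these are 1 and 0.866, so the noncentrality at 0.5 SD of change is about 0.5/(0.866 × √(2/35)) = 2.42. Averaging over chance baseline imbalance:

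| r | Power at 0.5 SD of change | 80% reached at, SD of change | Same, SD of a single score |
|---|---|---|---|
| 0.3 | 72% | 0.55 | 0.65 |
| 0.5 | 66% | 0.59 | 0.59 |
| 0.7 | 60% | 0.63 | 0.49 |

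Simulation with 40,000 replicates per setting agrees: 71.6%, 65.7% and 60.2% at 0.5 SD of change, with type I error between 4.9% and 5.1%.

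**The case against.** The strongest reply is that the randomised comparison is already planned. The ANOVA sentence comes directly after the paired-test sentence, which itself says that the test is before versus after in each group. A two-group before/after ANOVA has a group-by-time test equivalent to the change-score t test, which is a valid comparison. The sample size section names the paired formula openly, its figure is correct, and it never quotes 80% for a between-arm wellbeing test. Wellbeing is a secondary endpoint with an objective worded as exploratory, so formal power was optional. Any shortfall depends on an assumed effect: if scores worsen on water and improve on carbohydrate, the between-arm difference exceeds the within-arm change. With all 39 per arm analysed, 80% is reached at 0.64 SD.

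Much of this stands. No analysis is missing, 54% is not the trial's power, and ANCOVA is the more efficient choice rather than the only valid one. But the planned ANOVA does not correct the role given to the paired tests. The protocol also chose to claim 80% power in all its calculations and to say that one sample size serves both objectives, and it poses a formal hypothesis on wellbeing. These points limit the weight of the concern without removing it.

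**Conclusion.** The concern holds, as a should-fix point on a secondary, exploratory endpoint. The within-arm paired tests cannot determine the effect of the drink, and the objective 2 calculation covers only those tests. No power was derived for carbohydrate versus water on wellbeing. Whether that comparison is underpowered cannot be settled from the protocol: on change scores with 35 per arm it falls short of 80% only if the true difference is below 0.68 SD of change, or below 0.55 to 0.63 SD by ANCOVA for correlations of 0.3 to 0.7. The two-means calculation for gastric residual volume, the primary analysis and the total of 78 are unaffected.

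**What to change.** - **Data analysis.** For each VAS scale, make the test of the drink effect a between-arm ANCOVA of the before-OGDS score, with arm, before-drink score and sex (the stratification factor). Report the adjusted carbohydrate-minus-water difference with its 95% confidence interval. Give within-arm changes as description, not as the effect of the drink.
- **Expected result.** Keep the medians as description and add a column to the VAS table for the adjusted difference and its interval.
- **Sample size estimation.** Keep 78 subjects. State that the 80% for objective 2 applies only to the within-arm paired test, or withdraw it. State what 35 per arm can detect between arms with 80% power: 0.68 SD of change on change scores, or 0.55 to 0.63 SD by ANCOVA under the assumed correlations.

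The cost is wording in two sections and one table column. Both VAS scores and sex are already on the pro forma. The downside is that 80% power cannot be quoted for the between-arm wellbeing comparison at a difference of 0.5 SD of change.

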#### Secondary end point

- Score (mm) of each parameter from visual analogue scale (VAS) before drink and before OGDS for plain water and carbohydrate loading group

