### **Data collection method**

All subjected planned for OGDS with the complain of one or more of the following symptoms: Bothersome postprandial fullness, early satiation, Epigastric pain or Epigastric burning and fullfill inclusion criteria are selected. Patients will be approached and be explained regarding the study in

surgical outpatient clinic prior to OGDS. Patient will be approached again on the day of OGDS, if agree to participate, an informed consent will be obtained. Informed consent will be obtained after explanation regarding the study and procedure again by researcher nurse

Allocation sequence is according computer generated random number list, it was prepared by an investigator with no clinical involvement in the trial. Allocation sequence was concealed from researcher enrolling and assessing participants. Allocation sequence will be sealed in sequentially numbered and opaque envelopes. A manila card will be placed inside envelop to render it impermeable to intense light. To prevent subversion of the allocation sequence, the name and I/C of the participant will be written on a book together with the series number on envelopes. The details in the book will be kept confidentially. After enrolled subject complete all baseline assessment, corresponding envelope will be enclosed by staff (who not involve in study) who prepare the drink. The staff need to ensure that the envelop still sealed when receive it. The staff will prepare the drink into identical container according to the assignment.

Subjects are randomised into 2 group: 1 group with 250cc plain water and another group give 1 packet resource(237ml). Subjects need to finish the drink over 10minutes. After that, subjects are not allow to leave endoscope room before OGDS done to prevent consumption of other drink or food.

2 hours after that, subject undergo OGDS. OGDS is done follow standard protocol.

1. Patient lies in left lateral position
2. Medication to numb the back of throats (spray) will be given to prevent gagging during the passage of the instrument
3. A plastic mouth guard is placed between the teeth to prevent damage to the teeth and endoscope.
4. The endoscope (also called a gastroscope) will be inserted through the mouthpiece

[figure not shown]
5. A small container or yankauer suction is placed close to the mouth of a patient to collect saliva during and after the esophagogastroduodenoscopy
6. Endoscope will be inserted along the middle line of the soft palate.

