7. Once endoscope advanced, patient may be asked to swallow to facilitate advancement of scope.
8. Throughout the procedure, no water flushing is allowed, only air inflation is allowed
9. visualised pooling of fluid in the stomach is aspirated until dry via direct visualization with endoscope. Aspirated fluid will be collected in suction reservoir and the fluid will be measured.

Subject's wellbeing is assessed via visual analogue scale (VAS) which consist of 5 parameters: hunger, thirst, anxiety, tiredness and weakness. This scale will be used repeatedly during this study to assess patient's wellbeing. Trained staff nurse will ask patient regarding level of 5 parameters and subject need to mark X somewhere along the horizontal line given before drink and before OGDS procedure.

All subjects are advised to inform assessor if there is adverse reaction. Medical personnel are available to manage any adverse events that might occur throughout the procedure.

The possible risk that may arise in the study include injury to the gastrointestinal's wall, aspiration and bleeding which is the similar risk for all patient going through OGDS procedure. Small volume of the drink will not cause psychological distress to subject, but its taste may not be palatable.

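### Wellbeing is compared between arms by an unspecified ANOVA without baseline adjustment; ANCOVA on the pre-drink VAS score would be more precise at no cost

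*Protocol*

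**What the plan says.** The Data analysis section states the aim as "Objective 2 is to determine and compare subject's well being before and after drink in between group A and group B". Two methods follow. Within arms, "paired t test is used to determine effect of drink on subject's wellbeing before and after in each group". Between arms, "ANOVA is used to compare effect of the drink in both groups". The form of the outcome is not given, and no covariate is named here or elsewhere in the protocol.

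The data for an adjustment are already planned. The secondary endpoint is "Score (mm) of each parameter from visual analogue scale (VAS) before drink and before OGDS for plain water and carbohydrate loading group". Under Data collection method, the "subject need to mark X somewhere along the horizontal line given before drink and before OGDS procedure", for hunger, thirst, anxiety, tiredness and weakness. The same section fixes the order of events: "After enrolled subject complete all baseline assessment, corresponding envelope will be enclosed by staff (who not involve in study) who prepare the drink". I read the pre-drink VAS as part of that baseline assessment, so it precedes allocation.

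Randomisation is 1:1 and stratified by gender only (Research design; Sampling method and subject recruitment). The VAS table under Expected result shows medians with interquartile values for each arm and time, and no between-arm estimate.

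**The concern.** A score taken before allocation on the same scale as the outcome is usually the most useful covariate a small trial has. ANOVA can treat it in two valid ways. Applied to the pre-OGDS score, it leaves the baseline out, which amounts to fixing the baseline slope at 0. Applied to the change, or through the group-by-time term, it subtracts the whole baseline, which fixes the slope at 1. ANCOVA estimates the slope from the data.

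Two things are at stake for the between-arm wellbeing answer. The first is precision that the collected data could supply. The second is sensitivity to a chance difference in, say, baseline hunger. With 35 to 39 patients per arm and stratification by gender only, the design does not control such a difference.

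**Working it through.** **Inputs from the protocol (Sample size estimation).** Two-sided 5%, 80% power, 1:1 allocation. Objective 1: SD 18.46, difference 12.5, 35 per group. Objective 2: SD of paired differences twice their mean, 34 per group. Dropout 10%, giving 39 per group.

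**Reproducing the plan's figures.**
- Objective 1: n = 2 × (1.960 + 0.842)² × 18.46² / 12.5² = 34.2, so 35 per group. 35 / 0.9 = 38.9, so 39.
- Objective 2: standardised effect 0.5. The normal approximation gives (1.960 + 0.842)² × 4 = 31.4, so 32. The exact paired t test has power 0.795 at n = 33 and 0.808 at n = 34, so 34.

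The stated numbers hold. The 34 comes from a within-group formula, so it does not describe the between-arm wellbeing comparison.

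**Assumptions.** The protocol gives no pre/post correlation r, so I take r = 0.3, 0.5 and 0.7. Pre and post variances are taken as equal. Differences are in units of the SD of a single VAS score.

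**Formulas.** Variance of the between-arm estimate, relative to ANOVA on the final score:
- final score: 1
- change, or the group-by-time term with two time points: 2(1 − r)
- ANCOVA: 1 − r²

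Detectable difference with 35 per arm: (1.960 + 0.842) × √(2v/35), where v is the relative variance. For v = 1 this is 2.802 × 0.239 = 0.67 SD.

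| | r = 0.3 | r = 0.5 | r = 0.7 |
|---|---|---|---|
| Relative variance, final score | 1.00 | 1.00 | 1.00 |
| Relative variance, change | 1.40 | 1.00 | 0.60 |
| Relative variance, ANCOVA | 0.91 | 0.75 | 0.51 |
| Detectable difference, final score (SD) | 0.67 | 0.67 | 0.67 |
| Detectable difference, change (SD) | 0.79 | 0.67 | 0.52 |
| Detectable difference, ANCOVA (SD) | 0.64 | 0.58 | 0.48 |
| Power at a true 0.67 SD, change | 65.8% | 80.0% | 95.1% |
| Power at a true 0.67 SD, ANCOVA | 83.6% | 89.9% | 97.5% |

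A simulation of 4000 trials per value of r agrees: power 0.82, 0.89 and 0.97 for ANCOVA; 0.65, 0.79 and 0.94 for change; 0.79, 0.78 and 0.79 for the final score.

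**The ordering does not depend on the assumed r.** For any r strictly between 0 and 1, 1 − r² is below 1. Also 2(1 − r) − (1 − r²) = (1 − r)², which is above 0.

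**Chance imbalance.** The SE of a baseline mean difference is √(2/35) = 0.24 SD. Given a baseline gap g, the final-score estimate is shifted by r × g and the change estimate by (r − 1) × g. For a gap of one SE:

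| | r = 0.3 | r = 0.5 | r = 0.7 |
|---|---|---|---|
| Shift, final score (SD) | +0.07 | +0.12 | +0.17 |
| Shift, change (SD) | −0.17 | −0.12 | −0.07 |

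The two estimates differ by r × g − (r − 1) × g = g, the whole baseline gap. Which ANOVA is run can therefore alter the reported difference. ANCOVA removes the shift.

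**The case against.** The strongest reply is that the wording does not discard the baseline. Objective 2 speaks of before and after, the paired test ties the drink's effect to the change within each arm, and the endpoint includes both time points. That points to a change or group-by-time comparison. This stands, so change is the fair comparator. Against it the gain in detectable difference is 0.79 to 0.64 SD at r = 0.3 but only 0.52 to 0.48 SD at r = 0.7. The larger saving at r = 0.7 (relative variance 0.51 against 1.00) applies only against a final-score ANOVA.

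A second reply is that model form and covariates are commonly left to an analysis plan. That is fair for detail, but the protocol names its method for this comparison, and no valid reading of it adjusts for baseline as a covariate.

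Third, this is a secondary endpoint, worded under the specific objectives as exploratory. That limits the weight of the point without removing it.

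Three stronger inferences are not supported:
- **That the planned comparison is biased.** Under randomisation the final-score and change comparisons are both unbiased with correct type I error, and chance imbalance is already part of their standard error. What is lost is efficiency, and accuracy given the imbalance that actually occurs.
- **That a two-way ANOVA would be judged on its group main effect**, which dilutes the drink effect with the pre-drink scores. Nothing in the protocol says so, and its wording points to the change.
- **That a large baseline gap on at least one of five scales can be given a probability.** This needs the correlations among scales marked by the same patient at one sitting, which the protocol does not give.

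**Conclusion.** The point holds as a method choice that is loosely specified and less efficient than the planned data allow. Under every valid reading of ANOVA, adjusting for the pre-drink score is more precise. Against the best-supported reading, ANCOVA has 0.65, 0.75 and 0.85 times the variance at r = 0.3, 0.5 and 0.7 (0.91/1.40, 0.75/1.00, 0.51/0.60). Against a final-score ANOVA the ratios are 0.91, 0.75 and 0.51.

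These sizes rest on the assumed r, equal pre and post variances and 35 analysed per arm; the direction does not depend on r. The gain is modest at low r if the final score was meant, and modest at high r if the change was meant. The primary endpoint has no baseline measure and is untouched. The validity of the secondary comparison is not in question.

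**What to change.** In Data analysis, replace the ANOVA sentence with:

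> For each VAS scale the pre-OGDS score is compared between groups by ANCOVA with the pre-drink score and gender (the stratification factor) as covariates; the adjusted mean difference (mm) with 95% CI is reported.

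In the VAS table under Expected result, add that adjusted difference beside the medians, so that the display matches the mean-based analysis.

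The cost is one sentence and one table column. No new data, patients or staff are needed. The change also settles which between-arm analysis is meant, and should be made before outcome data are examined by arm.
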